#### Overview.

The study uses randomized waitlist-control design. We propose to randomly assign half of participants to (a) 10 weeks of MOBA intervention, and half of participants to (b) a 10-week waitlist, followed by 10 weeks of MOBA.

**Intervention.** MOBA is adapted from established protocols to integrate traditional behavioral activation (BA) principles with strategies to incorporate values-based, goal-directed movement into daily routines. The BA content of MOBA is adapted from co-investigator [name] intervention Behavioral Activation Therapy for Anhedonia (BATA). MOBA reduces depression-related content relative to BATA and increases focus on values that engage individuals in movement-related activity. MOBA is designed as a group intervention to leverage the reward value of social contact, and the positive influence of group problem-solving and accountability on behavior change. MOBA preserves the principles and general sequence of sessions used in BATA, but incorporates movement-oriented content: (a) provide psychoeducation about risks of physical inactivity, behavioral barriers to activity, and rationale for the treatment approach; (b) explore personal values, non-stationary, movement-oriented activities that support those values, and a hierarchical plan for goal attainment; (c) identify and assign weekly activities related to the valued goals; (d) address common barriers to engagement with valued activities including avoidance, low behavioral initiation, and an overemphasis on felt motivation as a prerequisite for action; and (e) monitor, support, and reward achieving behavioral goals. Content unique to MOBA includes: 1) demonstration and participation in physical activities that provide alternatives to stationary behavior, including select activities used in a previous study with the Dining Services cohort (e.g., stairs, body-weight squats, knee raises), and 2) generation of person-centered strategies for integrating movement-oriented activities into daily routines across the three domains of the Behavior Settings Model: 1) workplace sitting/prolonged standing, 2) screen-focused home activities, 3) time spent sitting in automobiles. Weeks 1-4 address topics a-c; weeks 5-12 address topics d-e. MOBA will be facilitated by a clinician ([name]) and a wellness educator ([name]), who will be trained on the MOBA treatment manual. The facilitators' role is to provide teaching, support, encouragement, and guidance throughout the intervention. Weekly sessions will take place in a dedicated conference room near the workplace, during the last hour of the workday (4-5 pm), and is counted as paid time at work.

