
#### Assessments.

**Pre-intervention focus group.** Separately, and prior to the enrollment in the intervention, we plan to conduct a small focus group of individuals (N = 8-10) from the Duke Dining Service staff in order to (1) better understand perspectives and experience with physical activity; (2) gauge interest in aspects of the study, and (3) understand format preferences for presenting and collecting information. The goal is to gather information to improve delivery of the intervention to participant stakeholders. Individuals who participate in the focus group are not under any obligation to participate in the intervention.

Feasibility and acceptability. We plan to collect multiple sources of information to provide information about feasibility and acceptability:

(1) We will document our challenges and decisions across all aspects of the study (e.g., recruitment, engagement, obstacles to enrollment) to optimize the translation of our findings; (2) We will collect descriptive data on adherence and participant engagement; (3) We will collect and characterize descriptive information on experience, perceived benefits, and satisfaction; (4) We will conduct focus groups with participants, and those who declined to participate, to better understand "what worked" and "what needs work" with respect to the intervention. We will consult with Duke Roybal Center intervention experts for input on our approach. Fidelity to the treatment will be assessed by [name], who does not lead groups, but will review taped sessions to document adherence (e.g., whether content described in treatment manual is presented during sessions).

Mobility testing. Short Physical Performance Battery (SPPB) will assess lower extremity function and mobility. The 6-Minute Walk Test (6MWT) will assess functional exercise capacity. These measures will occur at Baseline and Week 10.

Mechanisms of change. The Behavioral Activation in Depression Scale (BADS) will assess state characteristics of avoidance and activation. This measure will be administered at baseline and week 5. The Barriers to Being Active Quiz will assess perceived barriers to regular movement-oriented activity. These measures will be administered at baseline and post-intervention.

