## Selection of Subjects

- List inclusion/exclusion criteria and how subjects will be identified.

**Participants.** Inclusion: The pilot cohort will be composed of members of the Duke Dining Service staff age 30-64. The age range was chosen to target the critical window for establishing the long-term geroprotective benefits of increasing movement-oriented behaviors. The age range has also been expanded to allow for participation by all members of the Dining Service. The workplace cohort was chosen because their work demands are characterized by a high level of stationary activity, and because of previous success recruiting this group to participate in the Healthy Duke *Making the Connection* (MTC) wellness initiative. Additionally, 58% of this cohort reported >5 hours sitting per day, which indicates high levels of sedentary behavior in addition to stationary behavior at work. In MTC, the participating cohort was 72% female, and 80% were between age 30-64. Exclusion: 1) individuals with moderate or greater depression severity (PHQ-9 > 14); and 2) individuals with significant mobility limitation, defined as inability to complete 6 Minute-Walk Test. We plan to include rather than exclude individuals with medical comorbidities (e.g., diabetes, cardiac conditions, obesity) because this provides the most representative sample of the stationary population, and is consistent with our goal of developing a cross-cutting and translatable intervention. The Dining Services workforce is >90% African American, which is a group with disproportionately lower physical activity; and 3) individuals who answer "Yes" to any of the questions on the Physical Activity Readiness Questionnaire (PAR-Q) will be encouraged to consult with their physician before proceeding with the study. Physician clearance is not required for participation. Sample size. We plan to recruit 16 individuals for each of the two MOBA groups (N = 32), which allows for 23% attrition based on prior MTC completion rates.

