### Data Analysis & Statistical Considerations

- Describe endpoints and power calculations. Provide a detailed description of how study data will be analyzed, including statistical methods used, and how ineligible subjects will be handled and which subjects will be included for analysis. Include planned sample size justification. Provide estimated time to target accrual and accrual rate. Describe interim analysis including plans to stop accrual during monitoring. Phase I studies, include dose escalation schema and criteria for dose escalation with definition of MTD and DLT.

Sample size was based on previous recommendations from Lancaster et al. that targeting approximately 30 participants is a pragmatic standard for feasibility trials. While we recognize this sample size will not allow us to derive meaningful effect size estimates for between-group comparisons in this pilot study, it will be useful in determining the acceptability of the proposed intervention and deriving variance metrics (e.g., standard deviation of physical activity outcomes) for the purposes of future effect size estimation. We acknowledge that the proposed sample size is not adequate for formally testing group differences or effect size metrics. We will therefore (a) interpret these comparisons as preliminary, (b) characterize effect sizes for pre-to-post changes within each group separately, and (c) characterize group changes in actigraphy using contemporary minimum clinically important difference (MCID) metrics (e.g., 500 steps / day).

**Analysis plan for Aim 1.** We plan to collect multiple sources of information to provide information about feasibility and acceptability: (1) We will document our challenges and decisions across all aspects of the study (e.g., recruitment, engagement, obstacles to enrollment) to optimize the translation of our findings; (2) We will collect descriptive data on adherence and participant engagement; (3) We will collect and characterize descriptive information on experience, perceived benefits, and satisfaction; (4) We will conduct focus groups with participants, and those who declined to participate, to better understand "what worked" and "what needs work" with respect to the intervention. We will consult with Duke Roybal Center intervention experts for input on our approach. Areas of efficacy: We will use data from the PAST questionnaire to identify which domains of activity are most and least responsive to MOBA. Fidelity to the

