treatment will be assessed by [name], who does not lead groups, but will review taped sessions to document adherence (e.g., whether content described in treatment manual is presented during sessions).

**Analysis plan for Aim 2.** To test Hypothesis 2, we will examine mean difference in SPPB and 6MWT between baseline and post-intervention performance (e.g., student's *t*-test). We will also examine percent change and effect size (e.g., Cohen's *d*). To test Hypothesis 2b, we will compare change in self-reported sedentary time between baseline and post-intervention. We will plot and visually examine trends of change across monthly questionnaires. Additionally, we will examine change in Actigraph measures between baseline and post-intervention. As part of this aim, we will examine the association between self-report (PAST) and device-measured activity.

**Analysis plan for Aim 3.** To test Hypothesis 3, we will examine mean difference, percent change, and effect size in BADS (Avoidance and Activation scales) and BBAQ total score between baseline and post-intervention assessments.

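### Aims 2 and 3 ask a between-arm question, but no planned analysis adjusts for the baseline value, so an arm comparison built on the planned change scores would be less precise than it could be

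*Combined protocol and SAP*

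**What the plan says.** Participants are randomised: "We propose to randomly assign half of participants to (a) 10 weeks of MOBA intervention", with the other half waiting and then receiving MOBA. The Aim 2 and 3 hypotheses at the front of the document both predict greater change with MOBA than in the control group.

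The section Data Analysis & Statistical Considerations does not carry that contrast into a model:

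- **SPPB and 6MWT (Aim 2):** "we will examine mean difference in SPPB and 6MWT between baseline and post-intervention performance", with a t-test given as an example, plus percent change and Cohen's d.
- **Self-reported sedentary time (Aim 2):** "we will compare change in self-reported sedentary time between baseline and post-intervention".
- **Actigraph (Aim 2):** change between the same two points. The Assessments section names percent change in daily steps as the main device outcome.
- **BADS and BBAQ (Aim 3):** mean difference, percent change and effect size.

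No regression, ANCOVA, mixed model or baseline covariate appears anywhere. Baseline values are nevertheless scheduled. For the mobility tests, "These measures will occur at Baseline and Week 10". The note to Table 1 gives the waitlist arm a baseline, a pre-intervention and a post-intervention assessment.

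The plan is open about its limits: "We acknowledge that the proposed sample size is not adequate for formally testing group differences or effect size metrics". It keeps group comparisons all the same, and its first listed response is "a) interpret these comparisons as preliminary". Its second is to describe effect sizes within each group separately.

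**The concern.** Subtracting the baseline fixes the coefficient on baseline at 1. With equal variances at the two visits, the coefficient that minimises the variance is rho, the correlation between baseline and follow-up. When rho is below 1, the change score over-corrects: an arm that happens to start high tends to show a smaller rise, whatever the intervention did. In arms of about a dozen people, such chance differences are not small.

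At stake is the width of the interval around any preliminary arm difference. The same model would also yield the residual SD and the correlation, which suit the plan's stated aim of obtaining variance figures for a later trial. Adding only an arm t-test on change scores would supply the missing contrast but keep the loss of precision.

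**Working it through.** **The plan's own figures.** "We plan to recruit 16 individuals for each of the two MOBA groups (N = 32), which allows for 23% attrition" (Selection of Subjects). Arithmetic: 2 x 16 = 32; 32 x (1 - 0.23) = 24.6, or 16 x 0.77 = 12.3 per arm, taken as 12. The sample size rests on the view that "targeting approximately 30 participants is a pragmatic standard for feasibility trials". No alpha, power, SD or effect size is given, so there is no power calculation to reproduce.

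**Assumptions, because the documents are silent.** SD = 1 at both visits; rho from 0.3 to 0.9; n = 12 completers per arm; two-sided 5% level where power is shown.

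**Formulas for the variance of the arm difference.**

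- Change score: 2(1 - rho) x 2/n.
- Baseline-adjusted: (1 - rho²) x 2/n x [1 + 1/(2n - 4)]. The last factor is the price of estimating the slope; at n = 12 it is 1 + 1/20 = 1.05.
- Ratio, adjusted to change: (1 + rho)/2 x 1.05.

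| rho | SE, change | SE, adjusted | Variance ratio | SE reduction |
|---|---|---|---|---|
| 0.3 | 0.483 | 0.399 | 0.65 x 1.05 = 0.68 | 17% |
| 0.5 | 0.408 | 0.362 | 0.75 x 1.05 = 0.79 | 11% |
| 0.7 | 0.316 | 0.299 | 0.85 x 1.05 = 0.89 | 5.5% |
| 0.9 | 0.183 | 0.182 | 0.95 x 1.05 = 1.00 | none |

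Break-even: (1 + rho)/2 = 1/1.05, so rho = 0.905. Above that the variance penalty cannot exceed 5%. A simulation of 20,000 trials at 12 per arm agrees: the SD of the estimate falls from 0.482 to 0.397, from 0.408 to 0.362 and from 0.317 to 0.299 at rho 0.3, 0.5 and 0.7, and stays at 0.182 at rho 0.9.

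**Where the excess comes from.** 2(1 - rho) = (1 - rho²) + (1 - rho)². Slope estimation aside, the change score's extra variance is the term (1 - rho)², which is exactly the contribution of chance baseline imbalance.

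**Illustration of that term.** The arm difference in baseline means has SD sqrt(2/12) = 0.41. The chance that it exceeds 0.3 SD in either direction is 0.46. At rho = 0.5, an imbalance of 0.3 SD shifts the change-score estimate by (1 - 0.5) x 0.3 = 0.15 SD. In the simulation, the change-score estimate correlated with baseline imbalance at -0.60 (rho 0.3) to -0.22 (rho 0.9); the adjusted estimate did not.

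**What adjustment does not do.** For an illustrative difference of 0.5 SD at 12 per arm, simulated power moves from 17% to 22%, 22% to 26%, 33% to 36% and 74% to 74% at rho 0.3, 0.5, 0.7 and 0.9. At rho = 0.5, the difference detectable with 80% power (normal approximation) is 2.80 x 0.408 = 1.14 SD unadjusted and 2.80 x 0.362 = 1.01 SD adjusted.

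**The case against.** The strongest objection is that the plan never writes a change-score comparison between arms. The Aim 2 sentence reads most naturally as within-group, before against after, and the sample-size paragraph promises effect sizes within each group. A within-group mean change has no arm effect to estimate, so it has no precision to lose. This stands, and it limits the point: a reader might infer that the plan has chosen an inefficient arm contrast, but the documents do not show that. They state between-arm hypotheses, retain preliminary group comparisons and leave the contrast unwritten. The point concerns how that contrast should be written.

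A reader might also infer two harms, extra noise and a bias from imbalance. The decomposition above shows one loss. Under randomisation the change score is unbiased on average, and its ordinary standard error already includes the imbalance. The 0.15 SD shift is conditional on a given imbalance and should not be added to the loss of precision.

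Next, this is a pilot that disclaims formal testing, and no decision rule rests on the arm estimate. That lowers the stakes but does not answer the point, since what is asked for is an estimate with an interval, not a powered test.

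Finally, rho is unknown. A one-day recall or a single week of steps may well correlate only moderately over time, but the documents give no figure for any outcome and no basis for calling rho low for SPPB or 6MWT. The direction is secure below about 0.9; the size is not.

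**Conclusion.** The point holds as a cheap improvement that should be made. The hypotheses are between-arm, the written analyses are change scores without a baseline covariate, and an arm comparison built on them would have a larger variance than the adjusted one unless rho is about 0.9 or higher. Under equal variances and 12 completers per arm, adjustment cuts the variance by about 32%, 21% and 11% at rho 0.3, 0.5 and 0.7, and by nothing near 0.9.

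Two further inferences are not supported. The first is that adjustment would make N = 32 adequate for testing: power for a moderate difference rises by only a few percentage points, and results remain preliminary. The second is that every outcome can be adjusted with data already scheduled. For BADS, the Assessments section names baseline and week 5, while Table 1 and the Aim 3 analysis refer to post-intervention. For Actigraph, the Assessments section places the first wear in the week before MOBA participation, which for the waitlist arm could mean the end of the wait. Table 1's three waitlist timepoints suggest an earlier wear but do not settle it.

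**What to change.** In the Aim 2 and Aim 3 analysis paragraphs, state that the arm difference will be estimated at the common visit closing the first period: post-intervention in the MOBA arm, the pre-intervention visit in the waitlist arm. Use a linear model of the follow-up value on arm and the randomisation-baseline value of the same measure, and report the estimate with a 95% CI, labelled preliminary. Keep within-arm change, percent change and effect sizes as descriptive summaries.

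- **SPPB, 6MWT, PAST and BBAQ:** apply directly.
- **BADS:** first reconcile the week-5 schedule with the post-intervention analysis.
- **Actigraph:** first reconcile the wear schedule with Table 1, then apply the model where a randomisation-baseline wear and a common follow-up exist in both arms.
- **Visit label:** the Overview and Assessments sections use 10 weeks and the hypotheses 12; these also need reconciling.

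For the four outcomes that are ready, the cost is wording and one degree of freedom, with negligible loss of precision if rho is 0.9 or higher. For BADS and Actigraph, whether any extra collection is needed depends on how the schedules are reconciled.

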## Data & Safety Monitoring

- Summarize safety concerns, and describe the methods to monitor research subjects and their data to ensure their safety, including who will monitor the data, and the frequency of such monitoring. If a data monitoring committee will be used, describe its operation, including stopping rules and frequency of review, and if it is independent of the sponsor (per 45 CFR 46.111(a) (6)).

The study team includes three licensed clinical psychologists who will review any potential safety concerns at regular meetings, at least monthly. Other staff will be asked to report any potential safety concerns to the PI.

Adverse events will be systematically monitored at the time of enrollment, initiation of the study intervention, at the conclusion of the 6-month program. Although we anticipate few adverse events, we note that any intervention-related adverse events will be reviewed by the clinical team on a regular basis. For the purposes of the proposed study, an adverse event is defined as any undesired, noxious, or pathological change in a participant, as indicated by symptoms that occur in association with study participation. Pre-existing conditions that worsen during a study are considered adverse events. Serious Adverse Events (SAE) are defined as any adverse event that results in any of the following outcomes:

- Death or a life-threatening illness including active suicidal ideation/attempt (such as drug overdose)
- A persistent or significant disability/incapacity
- A requirement for hospitalization  $\geq 24$  hours

Participants will be screened with the PHQ-9 at enrollment, and those individuals with moderate or greater depression severity (PHQ-9  $> 14$ ) will be excluded; however, they will also be contacted for a wellness interview by the PI, and provided resources for care, such as Duke Personal Assistance Service.

All staff involved in the design or conduct of the study will receive and maintain the required education on the protection of human research participants prior to funding of the project. [name], [name], and [name] are all licensed clinical psychologists and will be available 24/7 for emergent and/or urgent study-related issues. Primary on call availability will be with [name], and [name] and [name] will provide back up as needed.

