Official Title: Movement-Oriented Behavioral Activation (MOBA) to Reduce Stationary Behavior

DUHS IRB Application Version 1.13

Pro00108020

Approval Date: 09/09/2022

NCT04892147

**Aim 1:** Determine feasibility and acceptability of a 10-week group MOBA intervention for individuals with excessive stationary behavior compared to waitlist control.

**Aim 2:** Assess activity and mobility changes following a 10-week group MOBA intervention for individuals with excessive stationary behavior compared to waitlist control.

**Hypothesis:** Individuals completing MOBA will have greater (1) improvement in physical performance, (2) reduction in sedentary time, and (3) increase in daily step count after 12 weeks compared to the control group.

**Aim 3:** Examine changes in activation, avoidance, and perceived barriers to physical activity after a 12-week group MOBA intervention for individuals with excessive stationary behavior compared to waitlist control.

**Hypothesis:** Individuals completing MOBA will have greater (1) increase in activation, (2) decrease in avoidance, and (3) decrease in self-reported barriers to physical activity after 12 weeks compared to the control group.

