Stationary behavior. With no validated questionnaire specific to stationary behavior, self-reported sedentary activity will be assessed at baseline/post-assessment, and weekly during the intervention using the Past-Day Adults' Sedentary Time questionnaire (PAST). The PAST assesses multiple domains of sedentary behavior over the past day; it was found to have the highest correlation to device-based activity compared to other questionnaires. The PAST will be administered at baseline, weekly, midpoint, and post

assessment. Device-based tracking. Participants will wear an Actigraph Actilife 6 accelerometer on the right hip for 7 days prior to MOBA participation. This period will represent the pre-intervention control activity condition for each participant. Participants will similarly wear the Actigraph for 1 week post-intervention. The main outcomes of device-based tracking will be percent change in step count per day, with secondary measures including total activity count, and physical activity energy expenditure.

MOBA intervention sessions will occur weekly.

The following questionnaires will also be administered. PHQ-9 will be collected at baseline and week 10, which is post assessment. Physical Activity Readiness will be collected at baseline. The Brief Health Questionnaire will be collected at baseline and week 10. At the final session, a MOBA Class Feedback form will be completed by the participants.

As shown in Table 1, participants will complete a baseline assessment administered by a fitness specialist that includes questionnaires and mobility testing. These assessments will be repeated at end of the intervention. Additionally, the wait-list control group will complete a third assessment at the end of their 02-week participation in MOBA.

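### The last systematic adverse-event check is tied to a six-month programme that fits neither arm, and no systematic enquiry is planned during the 10 weeks of MOBA

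*Combined protocol and SAP*

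**What the plan says.** Under Data & Safety Monitoring, the systematic checks are these: "Adverse events will be systematically monitored at the time of enrollment, initiation of the study intervention, at the conclusion of the 6-month program". The same section has licensed psychologists review safety concerns at least monthly, asks other staff to pass concerns to the principal investigator, and provides round-the-clock on-call cover. It counts the worsening of a pre-existing condition as an adverse event.

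The Overview under Design & Procedures assigns half of participants to "a) 10 weeks of MOBA intervention, and half of participants to (b) a 10-week waitlist, followed by 10 weeks of MOBA". Some 12-week wording survives beside this. Aim 3 speaks of changes "after a 12-week group MOBA intervention", and the session outline says "Weeks 1-4 address topics a-c; weeks 5-12 address topics d-e".

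The plan has many contacts during and at the end of MOBA. Sessions are weekly, and "MOBA will be facilitated by a clinician" together with a wellness educator. Of the mobility tests, Assessments says "These measures will occur at Baseline and Week 10"; of the activation and avoidance scale (BADS), "This measure will be administered at baseline and week 5". For self-reported sedentary time, "The PAST will be administered at baseline, weekly, midpoint" and again at the end. The PHQ-9 and the Brief Health Questionnaire are repeated at week 10, and the waitlist arm has a third assessment after its own MOBA. Participant Remuneration also budgets a 2-month follow-up interview for 32 people, without saying from what date the two months run. None of these contacts is described as an adverse-event enquiry.

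**The concern.** Of the three systematic checks, only the last can pick up events that arise on MOBA, and that is the one whose timing is described by a duration found nowhere else in the plan. Staff have to infer when to do it, and it has no definition by arm even though the arms finish about 10 weeks apart.

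The remaining routes act on concerns that someone has already raised. That matters because much of the activity takes place where staff cannot see it: Risk/Benefit Assessment expects participants to choose low-to-moderate activities in their own time. Selection of Subjects deliberately keeps people with diabetes, cardiac conditions and obesity, and does not require physician clearance. A strain or a symptom flare at home might not be mentioned in a group session.

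At stake is a dependable descriptive record of minor events from a pilot meant to inform later work.

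**Working it through.** **Step 1: can the six months be reproduced?** One month = 365.25 / 12 / 7 = 4.35 weeks, so six months = 26.1 weeks and two months = 8.7 weeks. The 10-week durations come from the Overview, the 12-week wording from Aim 3 and the session outline, the accelerometer weeks (one before and one after MOBA) from Assessments, and the interview from Participant Remuneration. Placing the interview after MOBA is an assumption.

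| Span | Weeks | Months (weeks / 4.35) |
|---|---|---|
| MOBA arm | 10 | 2.3 |
| Waitlist arm | 10 + 10 = 20 | 4.6 |
| MOBA arm with accelerometer weeks | 10 + 2 = 12 | 2.8 |
| Waitlist arm with accelerometer weeks | 20 + 2 = 22 | 5.1 |
| MOBA arm with interview after MOBA | 10 + 8.7 = 18.7 | 4.3 |
| Waitlist arm with interview after MOBA | 20 + 8.7 = 28.7 | 6.6 |
| 12-week wording, MOBA arm | 12 | 2.8 |
| 12-week wording, waitlist arm | 12 + 12 = 24 | 5.5 |
| 12-week wording, waitlist arm, with accelerometer weeks | 24 + 2 = 26 | 6.0 |

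The waitlist arm's first accelerometer week could fall inside the waitlist; its span is then 21 weeks rather than 22, or 25 rather than 26. No row built on the 10-week design gives six months. The near matches use the surviving 12-week wording: 24 weeks is six four-week months, and 26 weeks is six calendar months. Both describe the waitlist arm only. A leftover from a 12 + 12 week schedule is therefore the likely origin, but that is an inference.

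**Step 2: where the checks fall on the natural reading.** Take the initiation check as the start of each participant's own MOBA and the conclusion as its end, in weeks from randomisation.

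| | MOBA arm | Waitlist arm |
|---|---|---|
| Enrolment | about 0 | about 0 |
| Start of own MOBA | 0 | 10 |
| End of own MOBA | 10 | 20 |
| Checks strictly between start and end of MOBA | none | none |

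**Step 3: how long an event can go unasked.** For an event with onset t weeks into MOBA and a next check at week 10 of MOBA, the wait is 10 − t.

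- Longest wait: 10 − 0 = 10 weeks in either arm (10 − 0 = 10; 20 − 10 = 10 in study weeks).
- Average wait, if onsets are spread evenly over the 10 weeks (assumption): 10 / 2 = 5 weeks.
- A week-9 event is asked about after 10 − 9 = 1 week.

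With one added check at week 5 of own MOBA, the longest wait is 5 weeks and the average, on the same assumption, is 5 / 2 = 2.5 weeks.

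**The case against.** The strongest reply is that this is a wording slip in a low-risk pilot. The sentence anchors the check to an event, the programme's conclusion, and the six months only describes the programme; a sensible coordinator would ask at the end of MOBA. Participants see a clinician and a wellness educator every week, trained fitness specialists guide the activities, people who cannot complete the 6-minute walk are excluded, and anyone with a positive readiness answer is encouraged to see a physician. Adverse events appear in no aim, hypothesis or analysis. For 32 people doing low-intensity activity, spontaneous reporting plus monthly review is defensible.

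Most of that stands, and it limits the point. It does not supply a systematic enquiry during MOBA, and it does not make the stated duration right.

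A reader might infer more than the documents support in four ways:

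- **A very late last check.** Taken literally as 26 weeks from randomisation, the check would fall 26 − 10 = 16 weeks after MOBA in the MOBA arm and 26 − 20 = 6 weeks after it in the waitlist arm. That treats the descriptive duration as the schedule and sets aside the event to which the check is anchored.
- **A recall delay of at least 10 weeks.** On the natural reading, 10 weeks is the gap between checks and so the longest wait, not the typical one.
- **No contact after MOBA.** The 2-month follow-up interview may be such a contact; its starting point is not stated.
- **A biased comparison of adverse events between arms.** The plan makes no such comparison.

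**Conclusion.** The point holds in limited form. The six-month duration matches neither arm of the 10-week design, and the last check lacks a definition by arm. Read as the end of each participant's own MOBA, that check is well timed. What remains is a 10-week stretch in each arm without a systematic enquiry: an unvolunteered event waits up to 10 weeks to be asked about, and about 5 on average under evenly spread onsets. The documents give no event rate, so the number of events that might be missed cannot be estimated.

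The conclusion rests on the natural reading of initiation and conclusion as each participant's own, and on taking weekly sessions and questionnaires as described, that is, without adverse-event questions. The change should be made because it is cheap and improves safety capture in a cohort with medical comorbidities, although the underlying risk is low. No effect on the trial's efficacy results is claimed.

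**What to change.** In Data & Safety Monitoring, replace the six-month time point with the end of each participant's own MOBA: the week-10 assessment in the MOBA arm and the third assessment, at about week 20, in the waitlist arm. State that the initiation check also refers to each participant's own start.

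Add a short adverse-event question set, with onset dates, to the week-5 or midpoint questionnaire of each participant's own MOBA (study week 5 in the MOBA arm, about week 10 + 5 = 15 in the waitlist arm). If the 2-month follow-up interview takes place after MOBA, say so and ask the same questions there, so that an enquiry after the intervention is kept. Leave the enrolment check, monthly review, staff reporting and on-call cover as they are.

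Report events descriptively. List those found at the midpoint separately, because the waitlist period may have no matching contact.

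Cost: a wording change and a few minutes per contact, with no new visit. The midpoint check takes each participant from 3 systematic checks to 4, so (4 − 3) × 32 = 32 extra enquiries; using the interview adds up to 32 more, for at most 64. A few more minor events will be recorded and will need review.
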